
Eligible subjects were at least 18 years old, had the recessive form of DEB, and were NC1+. Each subject was on-study for approximately three months. Prior to administration, two wounds per subject < 10cm^2 in surface area were selected to be randomized to receive either KB103 or placebo. KB103 was administered at least 4 times between Day 0 and Day 30, both topically and intradermally.

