## 1.6 Rationale for Protocol Amendments

Four subjects were enrolled onto version 2 of the Phase 2 portion of the protocol. Three subjects (1 adult and 2 children) were administered 3e8 per wound daily for 5 days. One adult was administered 6e8 daily for 5 days. There were no signs of immunogenicity, no KB103-related adverse events and the data indicate that 3e8 per wound per administration was an effective dose for wounds 20 cm^2 or less.

Post-dose imaging from these patients clearly indicated that wound morphology and size is a major factor in wound healing as a result of KB103 administration. Wounds that were chronic but recurring based on natural history tended to heal and close completely within 7 to 10 days of KB103 administration. Chronic wounds that were open for a few years showed signs of healing following an initial five consecutive applications but the wound healing process appears to stagnate. These wounds would likely benefit from additional administrations to obtain full closure. Caregivers of the patients currently on trial have requested additional administrations to wounds that have clearly benefited but have not achieved complete wound closure.

Therefore, version 3.1 of the protocol incorporated dosing every 2 to 3 days for two weeks at 2e8 PFU with the option of at-home KB103 administrations, at the discretion of the Investigator.

Five patients were enrolled onto version 3.1 of the protocol. KB103 continues to be well tolerated and wound healing is observed in KB103 administered wounds. Wound healing results of the KB103 treated wounds evaluated to-date continues to show improvement. There is also empirical evidence that repeat administration on the chronic wounds that were retreated in patients that rolled over from the previous portion of the study showed improved healing with complete closure of the wound observed. Therefore, version 4.0 incorporates a 2-cycle approach to KB103 administration with greater flexibility given regarding the number of administrations within each cycle to understand the duration of treatment prior to moving into the Phase 3 Clinical trial.

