## 4 Study Design

### 4.1 Study Overview

This study is an intrasubject comparison of KB103-administered and placebo-administered wounds. Up to three 50 cm^2 areas will be selected for entry: one or two will be selected to receive topical KB103, and one to receive topical placebo.

The primary objective of this study is to evaluate clinical efficacy through digital imaging of wounds. Secondary objectives include an evaluation of change in an Investigator's global assessment and change in patient reported outcomes.

[figure not shown]
Patients will be administered Investigation Product (IP) in two cycles. Cycle 1 starts on Day 1. Up to three 50 cm^2 areas are administered IP (one or two KB103 and one placebo) every 2 to 3 days (to correspond with bandage changes) until wound closure, or up to 3 months. IP is administered to the entire areas, on the wound(s) and on intact skin.

Following this initial dosing period, patients will enter into an observation period in which wounds are monitored at home using a phone imaging app. Upon re-opening and/or expansion of a wound in the KB103 treatment area, patients will be asked to return to clinic or will be treated at home to begin the 2nd cycle of dosing.

The 2nd cycle mimics the first. The same 50 cm^2 areas are administered IP (one or two KB103 and one placebo) every 2 to 3 days until wound closure or up to 3 months. IP is administered to the entire areas, on the wound(s) and on intact skin.

After the 2nd cycle of IP administration, patients enter a second observation period. Patients image their wounds at home using a phone app, and return to the clinic at monthly intervals.

Time to wound closure and duration of wound closure will be evaluated after both the 1st and 2nd cycles. Safety will be monitored throughout the study.

Three additional new patients age 2 and older will be enrolled under this version. Patients from this protocol will be allowed to roll over into Phase 3 study of KB103.

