**Table 2 - Schedule of Events**

Procedures	Screen/ BL	Cycle #1		OP  #1	Cycle #2		OP #2			LTFU
		Dosing every 2-3 days	Home images		Dosing every 2-3 days	At-home monitoring and monthly on-site visits	C2 +1mo	C2 +2mo	C2 +3mo	
		≤ 3 months	Variable		≤ 3 months	3 months after C2 				
Urine Pregnancy Test	X									
HIV, Hep B, Hep C Testing	X									
Hematology & Chemistry 	X		X			X	X	X	X	
COL7 Antibody Assay	X		X			X	X	X	X	
HSV Antibody Assay	X		X			X	X	X	X	
Wound Area Assignment	X									
Pre-dose Tattoos	X									
Concomitant Medications	X	X	X		X	X	X	X	X	
Adverse Events	X	X	X		X	X	X	X	X	
Viral shedding (skin swab)	X	X	X		X	X	X	X	X	
Viral shedding (blood and urine)	X		X			X	X	X	X	
Physical Exam	X								X	
PRO Assessment	X	X	X		X	X	X	X	X	
Global Wound Assessment	X	X	X		X	X	X	X	X	
Vital Signs	X	X	X		X	X	X	X	X	
At-home wound imaging 		X	X	X	X	X	X	X	X	
On-site wound imaging	X	X	X		X	X	X	X	X	
Wound stenciling	X	X	X		X	X	X	X	X	
IP Administration	X	X	X		X	X	X	X	X	
Wound biopsy 	X		X			X	X	X	X	

 OP = Observation Period Visit windows for the OP2 visits are +/- 1 week After screening/baseline, performed only as clinically indicated to minimize blood draws At-home wound imaging occurs throughout the study during bandage changes Biopsies are performed at the discretion of the Investigator and Sponsor.

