### **6.3      Wound Area Selection**

Up to three wound areas are selected to be part of the study: one or two to receive KB103, and one to receive placebo. Final selection of the wound areas occurs at baseline. The following is considered when selecting target wound areas:

- **Wound areas can consist of one wound, or multiple wounds, and can include intact skin.**
- **The size of the wound area.** Target wound areas have a surface area up to 50 cm^2.
- **The location of the wound area.** Appropriate sites are on the anterior and/or lateral trunk and/or upper and/or lower extremities in areas protected from frequent trauma or injury. Excluded areas include the face, and areas close to mucous membranes (genitourinary, oral or anal mucosa).

- **The appearance of the wound.** Wounds should appear clean with adequate granulation tissue, excellent vascularization, and not appear infected.
- **Historical consistency in size of the wound.** A wound with a historically more consistent surface area is chosen over a less consistently sized wound.
- **The similarity of the wounds.** To the extent possible, similarity in location on the body should be considered.
- Wounds that have previously been administered investigational gene or cell therapy (except for previous KB103 administration) are not eligible for KB103 and placebo administration.

The Investigator will first selection two areas; one for KB103 and one for placebo. If another area meets the criteria above, it will be considered for inclusion in the study to receive KB103.

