## **6.5 Placebo Administration**

A wound area is selected to serve as the control at baseline. Topical placebo is administered on the days in which KB103 is administered. If KB103 is not administered to both of the KB103-selected wound areas on any dosing day, then placebo will not be administered. The dressings applied to the wound area that is administered the placebo gel mimic those applied to wound area administered KB103.

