## 14 Appendix 1 – KB103 Administration and Removal Instructions

### At-Home Administration Instructions

1. Open the compounding, dressing, cleaning and handling kits.
2. Put on the gloves provided with the cleaning and handling kit.
3. You will receive two KB103 vials for each wound to be treated. The vials are shipped on dry ice and stored in an ultra-low temperature freezer at the patient's home. Open the ultra-low temperature freezer and remove four KB103 vials. Inspect the vials for signs of leakage. If leakage as occurred, take a picture of the leakage and dispose of the vial in the provided red biohazard bag.
4. Place the KB103 vials on the blue towel provided in the cleaning and handling kit and let them sit for 20 to 30 minutes to allow the KB103 to warm to room temperature. **Do not let the vials sit for more than 40 minutes prior to use.**
5. The study team will tell you which of the wounds should be given KB103. If you are unsure, contact your study doctor or study coordinator.
6. Unpackage Mepitel One, Mepiform, Vaseline, and Kerlix Gauze dressings that were provided with the dressing kit and place them nearby. Prepare the wound for KB103 administration by unbandaging the area. Cut a hole in Mepitel One to the size of the wound to be treated and place the cut Mepitel on the patient's skin around the wound surface.
7. To compound KB103 with the gel, take one syringe and attached an 18G needle to it. Open a vial of KB103 and draw the product entirely into the syringe (each vial contains 200uL of KB103). Repeat the same procedure to draw the same volume of gel into a second syringe.
8. Activate safety cover of the needles and removes needles from syringes. Discard the needles in the sharp needle's container.
9. Join the two syringes using the guarded Luer lock connector.
10. To mix KB103 and gel (1:1 dilution), place the syringes in a vertical position and keep the syringe containing KB103 on top. Slowly dispense the syringe containing KB103 while drawing on the syringe containing the gel until all KB103 is mixed with the gel. Invert the syringes and repeat this operation twice.

11. Disconnect the syringes, keep the syringe containing the compounded product and apply directly to the patient's skin depressing the syringe plunger very slowly to cover the surface of the wound with KB103. Ensure that the KB103 is contained to the wound without any spillage.  

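### The SAP labels all Phase I/II work randomized, but protocol v4.0 describes no random draw and reserves any third wound area for KB103

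*Protocol*

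**What the plan says.** **SAP.** Section 3 describes the Phase I/II studies as randomized, and its version table includes v4.0 as row 2c. Section 8 calls the design a complete randomized block with the subject as block, and analyses subjects by randomized group. Section 1 says that the plan covers all data from Phase I through Phase II and that the study is not blinded.

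**Protocol v4.0.** Section 4.1 calls the study an intrasubject comparison in which "one or two will be selected to receive topical KB103, and one to receive topical placebo". Section 6.3 names who selects: "The Investigator will first selection two areas; one for KB103 and one for placebo". It then adds: "If another area meets the criteria above, it will be considered for inclusion in the study to receive KB103". Section 6.5 says: "A wound area is selected to serve as the control at baseline". Table 2 lists "Wound Area Assignment" at screening/baseline without a method. Appendix 1 tells caregivers only: "The study team will tell you which of the wounds should be given KB103".

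The only random allocation that the supplied protocol text describes for this study is in section 1.5, on the version 1.0 subjects, whose wounds "in surface area were selected to be randomized to receive either KB103 or placebo".

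**The concern.** If 6.3 is followed literally, the Investigator decides which wound area gets KB103 and which gets placebo. The SAP would then report as randomized a comparison for which the supplied protocol shows no random draw.

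Wound choice is prognostic by the protocol's own account. Section 1.6 calls wound morphology and size a major factor in healing: recurring wounds tended to close within 7 to 10 days, while wounds open for a few years stagnated. There is no blinding to offset this. SAP 8.1.1 leaves healing to the Investigator's determination, and under protocol 7.1.1 Investigators define wound area in the camera software.

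The bias could go either way. It favours KB103 if KB103 gets the easier wound. It works against KB103 if the product goes to the long-open wounds, of which section 1.6 says: "These wounds would likely benefit from additional administrations to obtain full closure".

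**Working it through.** **Text comparison**

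- First two areas: the SAP says randomized; v4.0 says that the Investigator selects, and is silent on any draw. The silence does not prove assignment by hand.
- Third area: the SAP's block design implies that each area could have received either treatment. Under 6.3 the third area can receive only KB103. This conflict is express.
- Earlier versions: v1.0 is described as randomized. The method for v2.2 and v3.1/3.2 is not visible in the supplied text, and nothing is claimed about it.

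**How much of the data is v4.0**

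The SAP section 3 table gives 2 + 4 + 5 + 3 = 14 subjects, matching the protocol synopsis (up to 14). The SAP also reports 12 subjects dosed, and section 4.1 gives enrolment as up to 12. Since 2 + 4 + 5 = 11 came under earlier versions, that leaves 12 − 11 = 1 under v4.0. Both cases are carried below.

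Wounds, KB103 vs placebo, with two KB103 areas per v4.0 subject:

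- 3 of 14: 2 + 8 + 10 + 6 = 26 vs 14
- 1 of 12: 2 + 8 + 10 + 2 = 22 vs 12

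**Possible size, first two areas (illustration only)**

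The documents give no rates, so every rate here is an assumption. Easier wounds close in 90% and harder ones in 30%, a gap of 60 points. A share m of pairs is mixed. KB103 goes to the easier wound of a mixed pair with probability q. The expected difference within a v4.0 pair, with no drug effect, is x = m × (2q − 1) × 60 points. Half of x raises one KB103 wound and half lowers the placebo wound, so the pooled shift is:

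- 3 of 14: 3(x/2)/26 + 3(x/2)/14 = 0.165x
- 1 of 12: (x/2)/22 + (x/2)/12 = 0.064x

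The standard error at 60% closure is √[0.24 × (1/n₁ + 1/n₂)], which gives 16.2 points (26 vs 14) and 17.6 points (22 vs 12). The one-sided error at nominal 5% is 1 − Φ(1.645 − shift/SE).

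| m, q | x | 3 of 14: shift, error | 1 of 12: shift, error |
|---|---|---|---|
| 0.30, 0.65 | 5.4 | +0.9, 5.6% | +0.3, 5.2% |
| 0.50, 0.75 | 15.0 | +2.5, 6.8% | +1.0, 5.6% |
| 0.50, 0.90 | 24.0 | +4.0, 8.1% | +1.5, 6.0% |

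If KB103 goes to the harder wound with the same probabilities, the shifts change sign and the error falls to 4.5, 3.6 and 2.9% (3 of 14) or 4.8, 4.5 and 4.2% (1 of 12). With no third area under v4.0 (23 vs 14), the weight is 0.172 and the shift 0.9 to 4.1 points.

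**Possible size, third area alone**

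Suppose that it closes d points more or less often than the other areas. The pooled shift is 3d/26 = 0.115d or d/22 = 0.045d. For d = 10, 20 and 30 this is ±1.2, 2.3 and 3.5 points (3 of 14), or ±0.5, 0.9 and 1.4 points (1 of 12).

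These figures treat wounds as independent at a single week. They do not reproduce the planned Cochran-Mantel-Haenszel test over weeks 8, 10 and 12.

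**The case against.** The strongest reply is that, for the first two areas, this is silence rather than contradiction. In the v1.0 account selection comes before randomization, so selection in v4.0 need not exclude a later draw. Table 2 lists assignment as its own entry, and the text on one area for each treatment can be read as a count. The SAP was written after a partial analysis and uses the past tense, so it may describe what was done. This stands: for the first two areas, the supportable statement is that v4.0 gives no method.

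It does not rescue the third area, which is added outside any draw. That point is narrow, though: the area is optional, must meet the same criteria, and there are at most three of them.

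Other limits also stand. The shared criteria in 6.3 narrow the differences between areas, although they ask for similarity only in body location and only as far as possible. Camera software and stencils limit subjectivity. The assumed rates have no source, and the range runs to both sides of zero, so no direction is shown. This is a pilot without a sample size calculation.

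The proposed baseline table partly overlaps existing plans: protocol 10.4 already summarizes baseline characteristics by treatment group. SAP 7.2 repeats that plan without the split by treatment, so the request is not redundant.

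**Conclusion.** The concern holds, for v4.0 only. Confidence is high that the SAP's blanket label conflicts with the v4.0 text: no random draw is described, and the third area is expressly KB103-only. Whether the first two areas were in fact drawn at random cannot be settled from the documents.

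The size and sign of any bias are unknown. The effect on the pooled result is probably small because v4.0 supplies few subjects; the illustrated shifts rest wholly on assumed closure rates, mixed-pair shares and assignment probabilities. The matter should be fixed because the report would otherwise misstate how the treatments were allocated.

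**What to change.** 1. **SAP wording.** In sections 3 and 8, state the allocation method for each protocol version. Remove the randomized and as-randomized descriptions wherever no draw was made. If a list exists for the first two v4.0 areas, cite it; the third area still needs its own statement.
2. **SAP analyses.** Tabulate baseline wound size, and wound history where recorded, by treatment. Add two sensitivity analyses of the closure results: one without any subjects found not to have been randomized, and one without KB103-only third areas. Keep the pooled p-value as planned, and report which subjects were not randomized.
3. **Protocol 6.3, only if a v4.0 subject is still unassigned.** Record all candidate areas with baseline size and history, then let a pre-made random list decide which is placebo, with any third area in the draw.

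Items 1 and 2 cost some wording, one table and two reruns, with no new data beyond recorded size and history. If all v4.0 subjects were left out (20 vs 11 wounds), the standard error would be 18.4 points: 13% wider than 16.2 (3 of 14), or 5% wider than 17.6 (1 of 12). Leaving out only their third areas gives 16.6 points (23 vs 14) or 17.7 points (21 vs 12), about 2% or 1% wider.

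Item 3 costs one paragraph and a short list. It helps at most 3 − 1 = 2 subjects, and none if enrolment ended at 12. Its downside is that the Investigator can no longer choose which selected area gets KB103.

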## 6.4 KB103 Administration

At-home topical administration of KB103 and placebo is performed as outlined in Appendix 1.

KB103 will be administered only if a target wound is visibly open. An opening as the result of biopsy will be considered visibly open wound. KB103 is compounded into a gel per the pharmacy manual.

On-site administration is performed as follows:

1. Unpackage the Mepitel One, Mepiform, Vaseline, and Kerlix Gauze dressings and place them nearby. Prepare the wound for KB103 administration by unbandaging the area. Cut a hole in the Mepitel One to the size of the wound to be treated and place the cut Mepitel on the patient's skin around the wound surface.
2. To apply KB103, while wearing gloves, apply the compounded product directly to the patient's skin by depressing the syringe plunger very slowly to cover the surface of the wound with KB103. Ensure that the KB103 is contained to the wound without any spillage.
3. If necessary, open a new syringe, connect the spreader and use it to spread the product on the patient's skin.
  - a. Any spillage on hard surfaces should be immediately wiped up with 10% bleach wipes, and any used wipes should be disposed of as a biohazard per standard operating procedure of the clinical site.
4. Let the KB103 sit for 5 minutes prior to placing any covering over the wound. Keep the area clean and do not touch the wound during the 5-minute period.
5. After applying KB103, remove the gloves, discard them in the biohazard container, and put on a new pair of gloves.
6. Cover the wound using the non-adherent side of the Mepiform above the wound and then cut to the full size of Mepitel dressings.

7. Thoroughly wrap the dressing in Vaseline Kerlix Gauze and further dress per standard of care.

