### 5.7.1 OP 2 Monthly Visits

At 30-day intervals (+/- 7 days) after the last administration of Cycle 2, the patient returns to the clinic for follow-up procedures:

- Adverse events
- Concomitant medications
- Vital signs
- Digital imaging of wounds
- PRO assessment
- Investigator's global assessment
- Collection of blood (approximately 10 mL) for clinical laboratory tests:
  - Serum chemistry
  - Hematology
  - Viral shedding
  - HSV and COLVII autoantibodies
- Collection of a skin swab for viral shedding analysis
- Collection of urine for viral shedding
- Month 3 only: physical exam
- Optional: Biopsy from a wound administered KB103 or placebo
- Wound stenciling
- If a target wound is open: Topical administration of KB103 and placebo to the target areas.

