## 5.8 Unscheduled Visits

Subjects may visit the clinic for unscheduled visits as deemed appropriate by the Investigator. Any or all of the monthly visit procedures may be performed during unscheduled visits.

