### 10.5.3 Target Wound Area

Target wound surface area is obtained through on-site and at-home imaging of target areas. Change in area from baseline is evaluated for using a paired t-test for each KB103 target wound vs. control wound.

Time to closure and durability of closure will be assessed after each cycle of administrations.

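### KB103 may be given during Observation Period 2, including to a closed wound opened only by an optional biopsy, and SAP 8.1.3 then counts the later closed time as duration of closure without a flag or censoring

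*Protocol*

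**What the plan says.** Protocol 6.4 makes a visibly open target wound the condition for giving KB103, then adds: "An opening as the result of biopsy will be considered visibly open wound". It makes no exception for OP2 or for a wound that was closed before the biopsy.

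Protocol 5.7.1 sets the OP2 visits: "At 30-day intervals (+/- 7 days) after the last administration of Cycle 2, the patient returns to the clinic for follow-up procedures". The procedures listed there include "Optional: Biopsy from a wound administered KB103 or placebo" and, later in the same list, "If a target wound is open: Topical administration of KB103 and placebo to the target areas". Table 2 marks both wound biopsy and IP administration at all three OP2 visits. Protocol 5.8 extends this to other visits: "Any or all of the monthly visit procedures may be performed during unscheduled visits". Protocol 7.2 leaves each biopsy to the discretion of the Investigator and Sponsor.

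Duration of closure is primary objective 1c (Protocol 2.1; also primary in SAP 2.2.1). Protocol 10.5.3 states: "Time to closure and durability of closure will be assessed after each cycle of administrations". SAP 8.1.3 measures duration from complete healing until the area reduction first drops under 90%, and compares treatments by analysis of variance. It does not mention doses given after closure.

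**The concern.** OP2 is the only window for durability after Cycle 2. If a closed KB103 wound is dosed in that window, what follows is closure after re-treatment, not closure that lasted off treatment. The SAP adds the two together.

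Placebo gel given on the same day does not balance an active dose. Under Protocol 6.5, placebo is withheld on a day when KB103 is not given to both KB103 areas, so a dose to one area of a subject with two could have no placebo counterpart at all.

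The SAP introduction describes the study as not blinded and biopsies are discretionary, so the number and timing of such doses are not fixed in advance. Version 4.0 was written to learn about treatment duration before Phase 3 (Protocol 1.6), which makes it useful to be able to read post-Cycle 2 durability cleanly.

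**Working it through.** The plan gives no figure to reproduce: Protocol 10.1 and SAP 4.1 say that no formal sample size calculation was done. The check is a reading of the text plus simple counts.

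**1. Is the dose permitted?** A wound that is already open meets the 6.4 condition without the biopsy sentence. That sentence therefore has effect only when the wound is otherwise closed. Section 5.7.1 lists the biopsy before the conditional dose at the same visit. Followed as written, biopsy of a healed wound leads to dosing.

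**2. Are there other routes?** Yes. The dose in 5.7.1 depends on one target wound being open but goes to the target areas in the plural. An open placebo wound, or an open second KB103 area, could lead to dosing of a KB103 area that is still closed. A KB103 area that is visibly open but still at least 90% reduced could also be dosed while the SAP counts it as closed.

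**3. Does any rule deal with the dose?**
- SAP 8.1.3: the clock ends only below 90% reduction, and there is no censoring.
- SAP 6.3 and Protocol 10.7: missing-data rules only (last observation carried forward; last measurement as endpoint).
- SAP 7.3: the dose enters exposure and compliance, with no link to duration.
- SAP 10.1: covers deviations, but a dose that 5.7.1 and 6.4 permit is not a deviation.

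**4. How much follow-up comes after such a dose?** Visits fall at 30k ± 7 days after the last Cycle 2 dose, for k = 1, 2, 3: days 23–37, 53–67 and 83–97.

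| OP2 dose at | Nominal days after it | Share of 90 days | Range across windows |
|---|---|---|---|
| Month 1 | 90 − 30 = 60 | 60/90 = 67% | 83 − 37 = 46 to 97 − 23 = 74 days |
| Month 2 | 90 − 60 = 30 | 30/90 = 33% | 83 − 67 = 16 to 97 − 53 = 44 days |
| Month 3 | 0 | 0% | no scheduled visit follows |

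**5. How many wounds?**
- Version 4.0: 3 subjects × 1 to 2 KB103 areas = 3 to 6. One area is 1/6 = 17% to 1/3 = 33%. Both areas of one subject are 2/6 = 33% to 2/4 = 50%.
- Pooled SAP, from the table in SAP section 3: 2 × 1 + 4 × 2 + 5 × 2 = 20 KB103 wounds in the earlier versions, plus 3 to 6, gives 23 to 26. One area is 1/26 = 3.8% to 1/23 = 4.3%. Two areas are 2/26 = 7.7% to 2/24 = 8.3%.

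Only wounds that reach closure contribute a duration. That number is not known in advance, so the shares among analysed wounds could be larger.

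**The case against.** The strongest reply is that OP2 was never meant to be free of dosing. Table 2 marks IP administration at every OP2 visit and 5.7.1 doses any open target wound, so the biopsy route is one corner of a wider gap. This stands. A remedy that flagged only biopsy-triggered doses would miss the others.

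Second, durability has a cleaner window. Protocol 4.1 says "Time to wound closure and duration of wound closure will be evaluated after both the" first and second cycles, and Observation Period 1 has no scheduled biopsy or dosing. This also stands. A reader might infer that primary objective 1c as a whole is compromised, but the documents support that only for the post-Cycle 2 part.

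Third, a reader might take 67% as a measure of bias, or 17–50% as the share of the SAP analysis affected. Neither is supported. The 67% is calendar time after a single application, in a regimen otherwise given every 2 to 3 days for up to 3 months, and the documents do not show what one dose adds to closure. The 17–50% applies to version 4.0 areas alone, whereas the SAP covers Phase I through Phase II.

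Fourth, a reader might infer that the biopsy hole itself would break the 90% rule. The documents give neither biopsy size nor baseline wound areas, so this cannot be established.

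Finally, the doses would not be hidden. SAP 6.1 lists all eCRF data, and with three new subjects dose dates can be set against closure dates by hand. What is missing is a rule fixed beforehand that ties the dose to the endpoint.

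**Conclusion.** The gap is real and minor. The protocol permits KB103 in OP2, including to a wound that was closed until biopsied, and SAP 8.1.3 counts closed time after that dose as duration of closure.

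The exposed portion is nominally 60 of 90 days after a month-1 dose or 30 of 90 after a month-2 dose. One affected area is 1 of 3 to 6 in version 4.0 and about 4% of the pooled wounds. The pooled figure assumes that all three planned version 4.0 subjects are enrolled and that every earlier subject had the number of KB103 wounds shown in the SAP table.

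Biopsies are optional, so the number of such doses may be zero, and the effect of one dose on closure is unknown. This is a pilot without a sample size calculation. What suffers is the interpretation of durability after Cycle 2, not an error rate.

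**What to change.** 1. On the dosing record, give the reason for every OP2 dose: natural re-opening or biopsy only. Identify the area that was open.
2. In SAP 8.1.3, for each KB103 area that is still closed apart from any biopsy site when it is dosed in OP2, censor duration of closure at that dose. Present this by Kaplan–Meier or as a per-wound listing, beside the uncensored result. Do not run analysis of variance on the truncated times, because that would treat a wound still closed at the dose as if it had re-opened.
3. State in the protocol and SAP that a marked biopsy site does not by itself count as re-opening or loss of closure.

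The cost is one extra field on the dosing record, a mark on the image and a few sentences of text. Observed follow-up in the censored analysis is slightly shorter. No visit or procedure is added, and biopsy sites can still be dosed.
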